#### 4.1 Conventions

The precision of original measurements will be maintained in summaries, when possible. Means, medians and standard deviations will be presented with an increased level of precision; means and medians will be presented to one more decimal place than the raw data, and the standard deviations will be presented to two more decimal places than the raw data.

---

 Mapped data consists of medical history, concomitant medication, and AE data obtained during the prior studies and imported into the 020 database (for handling of these data see Sections 5.5, 5.6, and 7.1, respectively).

Unless otherwise specified, summaries of continuous variables that have some values recorded using approximate values (e.g., < or >) will use imputed values. The approximate values will be imputed using the closest exact value for that measurement. For tables where rounding is required, rounding will be done to the nearest round-off unit. For example, if the round-off unit is the ones place (i.e., integers), values  $\geq XX.5$  will be rounded up to  $XX+1$  while values  $< XX.5$  will be rounded down to  $XX$ .

For percentages, unless they are calculated to be exactly 0% or 100%, values of very small or very large percentages will be reported as  $<0.1\%$  and  $>99.9\%$ .

For by-visit tables, percentages will be based on available data and denominators will generally exclude subjects with missing values. For frequency counts of categorical variables, categories whose counts are zero will be displayed for the sake of completeness. For example, if none of the subjects discontinue due to “lost to follow-up”, this reason will be included in the table with a count of 0.

## 4.2 Standard Calculations

Variables requiring calculation will be derived using the following formulas:

- **Baseline** - A baseline value, unless specified otherwise, is the last non-missing value recorded prior to the first dose of study drug in 020. If an assessment has the same date as the date of first dose of study drug in 020, the assessment will be counted as baseline (depending on the parameter, the data may have been acquired during the double-blind study of prior participation).
- **Study day** – For a given date (*date*), study day is calculated as days since the date of first dose of study drug in the open-label extension (*firstdose*):  
Study day =  $date - firstdose + 1$ , where  $date \geq firstdose$   
Study day =  $date - firstdose$ , where  $date < firstdose$
- **Days** – Durations, expressed in days, between one date (*date1*) and another later date (*date2*) are calculated using the following formula: duration in days =  $(date2 - date1 + 1)$ .
- **Weeks** – Durations, expressed in weeks, between one date (*date1*) and another later date (*date2*) are calculated using the following formula: duration in weeks =  $(date2 - date1 + 1) / 7$ .
- **Months** – Durations, expressed in months, between one date (*date1*) and another later date (*date2*) are calculated using the following formula: duration in months =  $(date2 - date1 + 1) / 30.4375$ .

- **Years** – Durations, expressed in years, between one date (*date1*) and another later date (*date2*) are calculated using the following formula: duration in years =  $(\text{date2} - \text{date1} + 1) / 365.25$ .
- **Body Mass Index (BMI)** -  $\text{BMI (kg/m}^2\text{)} = \text{weight (kg)} / [\text{height (cm)} / 100]^2$
- **Estimated Glomerular Filtration Rate (eGFR)** -  
 $\text{eGFR (mL/min/1.73 m}^2\text{)} = 175 \times (\text{serum creatinine in mg/dL})^{-1.154} \times (\text{Age in years})^{-0.203} \times (0.742 \text{ if female}) \times (1.212 \text{ if African American})$ .

Note that age on consent date is collected on the CRF and will not be calculated.

### 4.3 Handling Partial Dates

If only a partial date is available and is required for a calculation, the following standards will be applied:

- Start dates
  - a. For missing start day only in 020 - Day will be imputed as the first day of the month (i.e., 1) with the following exception: if the partial date falls in the same month and year as the date being used in the calculation (e.g., first dose date in 020, informed consent date for 020), then the partial date will be imputed to equal the date being used for the calculation. If the partial date is used for multiple calculations, then the earliest date will be used.
  - b. For missing start day and month in 020 - Day and month will be imputed as the first day of the year (i.e., 1 January) with the following exception: if the partial date falls in the same year as the date being used in the calculation (e.g., first dose date in 020, informed consent date for 020), then the partial date will be imputed to equal the date being used for the calculation. If the partial date is used for multiple calculations, then the earliest date will be used.
  - c. For missing start day only that is mapped from a previous study - Day will be imputed as the first day of the month (i.e., 1) with the following exception: if the partial date falls in the same month and year as the date being used in the calculation (e.g., first dose date, informed consent date), then the partial date will be imputed to equal the date being used for the calculation. If the partial date is used for multiple calculations, then the earliest date will be used.
  - d. For missing start day and month that is mapped from a previous study - Day and month will be imputed as the first day of the year (i.e., 1 January) with the following exception: if the partial date falls in the same year as the date

being used in the calculation (e.g., first dose date, informed consent date), then the partial date will be imputed to equal the date being used for the calculation. If the partial date is used for multiple calculations, then the earliest date will be used.

- Stop dates
  - a. For missing stop day only - Day will be imputed as the last day of the month (i.e., 28, 29, 30, or 31) or the last day of study contact if earlier
  - b. For missing stop day and month - Day and month will be imputed as the last day of the year (i.e., 31 December) or the last day of study contact if earlier

The date of last dose of study drug will be taken from the Study Exit Status CRF page. If this is missing, then the last visit date, excluding the follow-up visit, will be used, unless a data review indicates a different date. Similarly, if other key dates are missing, a review will be undertaken to aid imputation of these.

Any partial dates will be displayed in data listings without imputation of missing days and/or months (e.g., MAR2011, 2009).

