## **5.6 Concomitant Medications**

There are two CRFs contributing concomitant medication data.

- **Prior Study - Concomitant Medications CRF:** Concomitant medications as recorded during prior studies 005, 007 and 015 will be automatically uploaded to the Prior Study – Concomitant Medications CRF. These mapped medications will be available to the investigator at Visit 1 to use as a resource for completing the Concomitant Medications CRF. Concomitant medications recorded during the 008 study will be recopied from the 008 records by the site to the Prior Study – Concomitant Medications CRF.
- **Concomitant Medications CRF:** During Visit 1, all medications that were ongoing at the end of the prior study will be recopied by the site to the Concomitant Medications CRF. At each visit, any changes to existing concomitant medications and any new concomitant medications will be reviewed and recorded in the Concomitant Medications CRF. The date of commencement, dose, and date of any change of dose of concomitant medications are to be recorded.

Verbatim terms on case report forms will be coded to Anatomical Therapeutic Chemical (ATC) classes and Generic Drug Names using the World Health Organization (WHO) dictionary (WHODDE B2, March 1, 2013 release). The coding process is described in the Data Management Plan.

Each of the below summaries will be presented for each of the following:

1. Concomitant medications that were ongoing on Day 1 of dosing (pre-existing) - source is the Concomitant Medications CRF.
2. Concomitant medications that started on or after Day 1 of dosing (study-emergent) - source is the Concomitant Medications CRF.
3. All concomitant medications, whether pre-existing or study-emergent (merge of ongoing medications from the Prior Study - Concomitant Medications CRF and medications that were ongoing on Day 1 of dosing and medications that started on or after Day 1 of dosing from the Concomitant Medications CRF).

Concomitant medications will be summarized by WHO ATC classification level 1 term, ATC level 3 term and Preferred Term (generic name) with frequency and percentage of subjects. At each level of subject summarization, a subject is counted once if he/she reported one or more medications at that level. Each summary will be ordered alphabetically by each level of ATC class and generic drug name within each level of ATC class.

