## **7. SAFETY ANALYSES**

### **7.1 Adverse Events**

There are two CRFs contributing adverse event data.

- **Prior Study – Adverse Events CRF:** All adverse events as recorded during prior studies 005, 007 and 015 will be automatically uploaded to the Prior Study – Adverse Events CRF and adverse events recorded during the 008 study will be recopied from the 008 records by the site to the Prior Study – Adverse Events CRF. The only field that can be modified by the site is the OLEX end date as applicable. Additionally there is a comment field where text can be entered by site.
- **Adverse Event CRF:** New adverse events or changes to an existing adverse event will be recorded on the Adverse Event CRF.

Adverse events will be coded to SOC and PT using MedDRA (version 16.0). The coding process is described in the Data Management Plan.

AEs are grouped as follows and source(s) of data identified:

1. **Prior AEs:** AEs that were ongoing at the end of the prior study but that resolved before Day 1 of dosing in 020 or that started and resolved during the gap between studies. The source would be both the Prior Study – Adverse Events CRF and the (020) Adverse Event CRF.
2. **Pre-existing AEs:** AEs that were ongoing on Day 1 of dosing in 020 - source is the Prior Study – Adverse Events CRF. The source would be both the Prior Study – Adverse Events CRF and the (020) Adverse Event CRF.

3. Study-emergent AEs: AEs that started on or after Day 1 of dosing in 020, excluding post-treatment AEs (defined in #5 below). The source would be the (020) Adverse Event CRF.
4. All AEs: Whether pre-existing or study-emergent (merge of AEs that were ongoing on Day 1 of dosing) excluding post-treatment AEs. Sources are the Prior Study – Adverse Events CRF and the (020) Adverse Event CRF (note, this is a merge of #2 and 3 above *only*).
5. Post-treatment AEs: The study-emergent AEs (3# above) that have an onset more than 14 days after the last dose of study drug or that worsen in intensity or treatment attribution following discontinuation more than 14 days after the last dose of study drug.

The tabular summaries will be provided for AEs, with the number and percentage of subjects reporting each type of event. If a subject reports the same preferred term more than once, it is counted only once within that category. Further, for a given tabulation, the preferred term will only be counted once at its worst severity and strongest relationship to treatment.

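### SAP 4.3 can move a partial start date to the first 020 dose against evidence in the record, so some gap AEs start after they stop and some recopied drugs count as newly started

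*SAP*

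**What the plan says.** SAP 4.3, start dates, rules a and b, cover records entered in 020. The default is the first of the month if only the day is missing, and 1 January if day and month are missing. Both rules carry an exception. Rule a applies it "if the partial date falls in the same month and year as the date being used in the calculation"; rule b applies it "if the partial date falls in the same year as the date being used in the calculation". In those cases "then the partial date will be imputed to equal the date being used for the calculation". First 020 dose and 020 consent are the named examples of such dates. Each rule closes with a tie-break: "If the partial date is used for multiple calculations, then the earliest date will be used".

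The classes that use these dates are defined elsewhere:

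- **AEs (SAP 7.1).** The study-emergent class is "AEs that started on or after Day 1 of dosing in 020, excluding post-treatment AEs", drawn only from the 020 AE form. The Prior class includes AEs "that started and resolved during the gap between studies", and the 020 AE form is one of its sources.
- **Medications (SAP 5.6).** At Visit 1 "all medications that were ongoing at the end of the prior study will be recopied by the site to the Concomitant Medications CRF". The study-emergent medication table draws on that same form and selects by a start no earlier than Day 1. Prior medications are those stopped before the first 020 dose.

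Protocol 9.4 asks for medications already in use at study start and newly begun ones. Protocol 9.6.1 treats AEs that resolved before first dose as pre-treatment and leaves them out of the summaries.

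**The concern.** Setting an uncertain AE onset to the first dose is a familiar and cautious convention. It is reasonable when nothing in the record says otherwise. Here it also applies when the record does say otherwise: a known stop date before first dose, or a drug that is on the 020 form because it was already in use at the end of the double-blind study. Nothing in SAP 4.3 stops the imputed start from contradicting that evidence.

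At stake is whether the study-emergent AE and medication tables mean what their titles say. Long-term safety is a primary objective, and these tables report it. SAP 7.1 also counts repeat AEs on dates after imputation, so a start later than its own stop can disturb event counts as well.

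**Working it through.** The plan states no figure to reproduce. The check applies rules a and b and the class definitions to hypothetical records, with an assumed first 020 dose of 20SEP2015. I read the tie-break as taking the earliest matching reference date.

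| Record on a 020 form | Reference date(s) | Imputed start | Class by definition |
|---|---|---|---|
| AE, start SEP2015, stop 12SEP2015 | first dose only | 20SEP2015 | Prior and study-emergent |
| same | first dose, consent same day | 20SEP2015 | Prior and study-emergent |
| same | first dose, consent 10SEP2015 | 10SEP2015 | Prior |
| AE, start SEP2015, ongoing | first dose only | 20SEP2015 | study-emergent |
| same | first dose, consent 10SEP2015 | 10SEP2015 | pre-existing |
| Recopied drug, start 2015, ongoing | first dose only | 20SEP2015 | study-emergent |
| same | first dose, consent same day | 20SEP2015 | study-emergent |
| same | first dose, consent 10SEP2015 | 10SEP2015 | pre-existing |
| Drug, start AUG2015, ongoing | any of the above | 01AUG2015 | pre-existing |
| Drug, start 2014, ongoing | any of the above | 01JAN2014 | pre-existing |

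**Gap AE.** Imputed start minus stop = 20 − 12 = 8 days, so the event begins after it ended. It meets the Prior definition by its stop and the study-emergent definition by its start. The SAP gives neither class precedence.

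**Recopied drug.** Its presence on the form as a carry-over shows use before 020, yet its imputed start is Day 1.

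**Largest forward move from the section's own default.** Rule a: day 31 − day 1 = 30 days. Rule b: 31 December − 1 January = 364 days in a non-leap year.

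**Share of recopied year-only starts exposed (assumption only).** Suppose such starts fall evenly over the W months before first dose, with W at least 12, and first doses fall evenly over the calendar year. The chance that start and first dose share a year is the average of u/W for u from 0 to 12, which is 6/W. That gives 6/12 = 50%, 6/18 = 33% and 6/24 = 25%. Starts older than W months are left out by construction, so this is not a share of all recopied drugs.

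**With the guard described under the fix.** The gap AE goes to 01SEP2015 and is Prior only. The recopied drug goes to 01JAN2015 and is pre-existing. The ongoing AE with no contrary evidence stays at 20SEP2015 and is study-emergent.

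**The case against.** The strongest reply is the tie-break. Consent is a named reference date, and if an earlier matching consent date counts, neither problem record is study-emergent. That stands as far as it goes. But the SAP does not say whether consent counts when AEs and drugs are classified. Consent and dispensing are both scheduled at Visit 1, and the clause changes nothing when consent and first dose share a day. It also does not ensure a possible date: with a stop of 08SEP2015, a start at consent on 10SEP2015 would still be 2 days too late. And it would take the ongoing AE out of the study-emergent class, which gives up the cautious default.

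A second reply is that AE recording starts at consent (Protocol 7.1), so few gap AEs reach the 020 form. That narrows the route but does not close it. Protocol 4.4 asks for AEs to be updated when Visit 1 does not coincide with the last double-blind visit, and SAP 7.1 provides for gap AEs.

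Third, the analyses are descriptive, listings show partial dates unimputed, and a move between pre-existing and study-emergent leaves the combined tables unchanged. This limits the harm, mainly for medications. It does not cover the gap AE: the combined AE table merges only the pre-existing and study-emergent classes, so a Prior AE that also counts as study-emergent is added to it. The review of missing key dates in SAP 4.3 does not mention partial AE or medication dates.

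A reader might infer three stronger things that the documents do not support:

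- *That long-standing drugs in general become study-emergent.* The exception needs the month and year, or the year, of first dose. Participation lasted 19 months (005), 16 months or about 13 without the extension (015), and 12 months (007), so a drug begun before those trials normally carries an earlier year. Study 008 is the exception, at 2 months, with 9 subjects randomised.
- *That AEs carried over from the prior trial become study-emergent.* The mapped prior-study AE form is not a source for that class.
- *That every exposed gap AE is misclassified.* Such a record also meets the Prior definition, so its class is contradictory rather than plainly study-emergent.

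**Conclusion.** The point holds in a limited form. Rules a and b override evidence in the record when the partial date matches the month and year, or the year, of first dose and first dose is the operative reference date or consent is on the same day. A gap AE on the 020 form with a known stop before first dose then has two classes and an impossible date sequence. A drug recopied as ongoing, and begun in that same month or year, can be tabulated as newly started.

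The number of affected records is unknown, because the documents give no count of partial dates. The 25% to 50% range rests on assumed spreads of dates and applies only to recopied year-only starts within the last 24 to 12 months. No inference is at risk, since the study is descriptive. It is still worth correcting, because a stated rule, followed literally, gives a wrong result in safety tables.

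**What to change.** Add to SAP 4.3, to be applied before any classification:

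1. An imputed start may not be later than the record's stop date (itself imputed if partial). If it would be, use the section's own default, the first of the month or 1 January. A record that stopped before the first 020 dose is classed as prior only.
2. A medication recopied as ongoing at the end of the prior study is classed as pre-existing, except for a dose change or new regimen recorded in 020.
3. For AEs with no contrary evidence, keep the first 020 dose as the default, and name it as the reference date for classification.

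The second rule should not be extended to AEs. Changes to an existing AE are entered on the 020 AE form, and Protocol 9.6.1 counts worsening on treatment as treatment-emergent. Forcing such records to a start before 020 could hide a true worsening.

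The cost is a few sentences and a small programming change, with no new data. The SAP describes no field that marks a medication line as recopied. If the form has none, those lines must be matched by subject and drug to the prior-study medication form.

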#### **4.4 Visit Windows**

Since study visits do not always take place exactly as scheduled in the protocol, it is necessary to assign the actual observation times to “analysis visit windows” for analysis purposes. Post-baseline visit windows for each target visit are defined in [Appendix A](#), and will be applied to all measurements. For each summary and value if there are multiple values within a visit window, the “worst” value as defined in [Appendix D](#) will be used for that visit window summary. These visit windows will be applied to all visits, including scheduled, unscheduled, and early termination visits.

